Executive function deficits are common in late life depression. They are associated with resistance to antidepressants, poor quality of life, considerable disability and increased risk for suicide. No optimal treatments exist for this problem. Selective serotonin reuptake antidepressants do not improve executive impairments and psychotherapy is less helpful with co-occurring executive deficits. Therefore, a safe and well-tolerated treatment is needed to improve executive function, depression burden and overall quality of life. This study will use a novel type of Transcranial Magnetic Stimulation called intermittent Theta Burst Stimulation (iTBS). iTBS uses very high frequency (50Hz) magnetic pulses delivered in “bursts” of 3 stimuli delivered at 50 Hz. It is posited that this intervention induces plasticity in the human cortex. Theoretical and empirical evidence from research studies informs that iTBS is can also improve depression and executive deficits. However such effects have not been examined in older adults.

This project examines iTBS’s ability to improve depression and executive impairment in Late life depression (LLD). In addition the study tests the effects of iTBS on brain connectivity within the Cognitive Control Network (CCN). This study will enhance the understanding of LLD and will provide critical pilot data regarding feasibility to support the development of future randomized controlled clinical trial.

Both active and sham (placebo) interventions will be administered sequentially to the left and right dorso-lateral prefrontal cortex. The total time of stimulation or sham is less than 7 minutes. Active or sham intervention will be administered for 6 weeks (Monday to Friday). A total of 20 subjects will be randomized. Changes in mood from baseline to the end of 6 weeks will be measured using The Montgomery-Asberg Depression scale. Executive function at baseline and end of study will be evaluated with the National Institutes of Health (NIH) Toolbox executive domain battery. Safety assessments will include: The 21 item Scale for suicidal ideation SSI. The frequency, intensity and burden of side effects rating (FIBSER) and the Altman Self Rating Mania scale (ASRM). Ancillary depression measures include the The self-reported Quick Inventory of Depressive Symptoms (QIDS) and the Clinical Global Impression of Improvement scale.

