Subject's termination from study by PI will be documented in Case report forms.

2.h Data Collection and Follow-up for Withdrawn Subjects

All data collected from subjects up to their withdrawal date will be used for analysis.

If a subject decides to withdraw, we will ask him/ her to come for a close out visit to complete the same mood and executive function assessments that were recorded at baseline.

D3 Study Device: rTMS device

3.a Description of the rTMS device used to deliver iTBS vs sham (placebo)

We will use the rTMS device currently available at our institution for clinical and research applications. The stimulator is a MagPro R 30 magnetic stimulator manufactured by MagVenture A/S (Farum, Denmark) and FDA approved for treatment of major depressive disorder. Equipment components include: 1) R30 magnetic stimulator 2) coil cooler unit 3) dedicated C-B60 butterfly coil for Motor threshold assessments only 4) Treatment chair with neck rest and cloth cover, subjects will recline in this comfortable motorized recliner during intervention delivery 5) Head Stabilizer System (Airtight Pillow and Evacuation Pump).

The intervention will be delivered using:

- A Coil- cool B65 A/P butterfly coil. This coil functions as both active and sham coil. The coil has a symmetrical design, one side of the coil delivers active treatment and the other side delivers sham. Both sides of the coil are identical.
- Theta burst delivery software
Maglink software, this software interfaces with the B65 A/P coil to deliver the randomization assignment. The software provides codes assignments according to the randomization schedule to ensure double -blind conditions

The Magpro R30 is a non-significant risk device because:

- It is not an implant
- It is not for use in supporting or sustaining human life
- It does not present a potential for serious risk to the health, safety or welfare of study

3b. Other devices used:

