Subjects assigned to iTBS: Burst of three stimuli at 50 Hz, repeated every 200ms using a two-seconds train repeated every 10 seconds for a total of 190s (600 pulses). TBS will be delivered over the scalp over the brain area corresponding to the dorsolateral prefrontal cortex. We will apply stimulation bilaterally with a total of 600 pulses on the left and 600 pulses on the right. This protocol takes about 8 minutes to complete.

Subjects assigned to Sham: Stimulation will be delivered mimicking the pulse

frequency, sound and sensation of the active stimulation but with not active magnetic pulse delivery.

Intervention delivery # 2- 30: Subsequent interventions will be scheduled daily Monday to Friday the theta burst stimulation paradigm as described above will be used.

Weekly assessments:

We will obtain the following assessments on a weekly basis, at the end of the intervention week.

Montgomery Asberg Depression Rating Scale (Week 2, Week 4, and Week 6 only*)

Quick Inventory of Depressive Symptoms Self report

21 item for suicidal ideation (SSI)

Frequency Intensity and Burden of side effects (FIBSER)

Altman Self Rating Mania Scale (ASRM)

NIH Toolbox – General Life Satisfaction CAT and Positive Affect CAT (Baseline, Week 2, Week 4, and Week 6 only*)

Anxiety Measure (self-report) (Baseline, Week 2, Week 4, and Week 6 only*)

Ruminative Response Scale (RRS) (self report) (Baseline, Week 2, Week 4, and Week 6 only*)

End of intervention assessments:

At the end of 6 weeks, or 30 interventions we will repeat the NIH Tool box battery, Semantic Fluency, Trail Making Test, FrSBE, the Revised Observed Tasks of Daily Living (OTDL-R), Delis-Kaplan Executive Function System (D-KEFS): Color-word interference, the California Verbal Learning Test – second edition (CVLT-II), and the Line Orientation test from RBANS in addition to the weekly assessments. This assessment session will take about three hours to complete.

Post-intervention MRI Scan Visit

Neuroimaging Pre-Scan Questionnaire

Post-intervention MRI scan (about 60 minutes)

This visit will take one hour and half to complete.

E3 Safety and Adverse Events

Interventions and precautions to minimize subject's risk during TBS intervention:

- Treating personnel is trained to act as first line responder, and will have cardiopulmonary resuscitation (CPR) training, in case of a seizure event.

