Statistical Analyses: We will use intention-to-treat principles. We will use t-test or its non-parametric equivalent to compare the distribution of continuous variables and the changes in the main outcome measures between active and sham groups. χ^2 tests will be used to compare categorical variables between groups. We will use a mixed general linear model (GLM) to accommodate data from our within- and between-participant study design to examine changes from baseline to post-intervention, and compare them between active vs. sham groups. The GLM explores estimated marginal means by taking into account within- and between-participant variability, adjusting for confounders and allowing exploration of significance of within-participant and between-group interaction effects. Differences between groups in behavioral outcome measures and network connection changes will be evaluated through 2-way interaction effect (time*group). Through the 2-way interaction iTBS*Fazekas score we will explore the modification effect of grade of white matter burden on the impact of iTBS in the observed network connectivity changes. Pearson's correlation will examine the correlation between changes in behavioral measures with changes in network connectivity. We will use Hayes' PROCESS¹¹⁴ macro to evaluate the role of the difference in the strength of connections pre-intervention minus the strength of connection post intervention as mediator of change for iTBS and bootstrap and Monte Carlo confidence intervals will be calculated. All statistical tests will be two-sided and evaluated at the alpha level of 0.05. SAS 9.4 (SAS Institute, Cary, NC) and R 3.2.3 statistical software packages will be used for all analyses. Sample size justification: For this pilot study, I plan to enroll 20 elderly subjects and randomized them to iTBS arm or placebo arm (10 in each group). The sample size of 20 subjects is feasible for the time limit of the KL2 award. This pilot sample will provide meaningful data to estimate sample size and calculate power for a subsequent grant application to rigorously test the effects of theta burst stimulation on depressed older adults.

G Data Handling and Record Keeping Records retention:

Study data will be kept for potential future analysis. Records will be maintained for at least 7 years after completion of the study as per local HRPO requirements.

G1 Confidentiality and Security

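### Section F does not say that the week 2 and week 4 MADRS scores enter any analysis, so the Section 2.h commitment to use all data up to withdrawal is not carried through

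*Combined protocol and SAP*

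**What the plan says.** MADRS is a primary outcome (E4). The abstract (A1) fixes the time frame: "Changes in mood from baseline to the end of 6 weeks will be measured using The Montgomery-Asberg Depression scale". The schedule in E2 collects it in between as well: "Montgomery Asberg Depression Rating Scale (Week 2, Week 4, and Week 6 only".

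Section F names two analyses that could apply to MADRS. One is a simple comparison: "We will use t-test or its non-parametric equivalent to compare the distribution of continuous variables and the changes in the main outcome measures". The other is a mixed general linear model "to examine changes from baseline to post-intervention, and compare them between active vs. sham groups", in which group differences in behavioural outcomes "will be evaluated through 2-way interaction effect (time*group". F does not list the levels of time, does not say which of the two analyses is primary, and gives no rule for a missing week-6 value.

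Two commitments bear on subjects who leave early. F states "We will use intention-to-treat principles". Section 2.h states "All data collected from subjects up to their withdrawal date will be used for analysis". For anyone who leaves by their own choice, the same section adds this: "we will ask him/ her to come for a close out visit to complete the same mood and executive function assessments".

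**The concern.** The interim scores are the only on-treatment clinician ratings of depression for a subject who stops before week 6 and has no close-out visit. As F is worded, nothing brings them into the comparison. A subject with no post-intervention MADRS has no change score and drops out of the t-test or rank test. In a mixed model with only two time points, that subject adds a baseline value and nothing about response.

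This matters if leaving is related to early response. A subject hospitalised for depression is terminated under E3, and one who is not improving may stop attending. If leaving depends on weeks 2 and 4 and those scores are left out, the week-6 contrast is in effect a comparison of completers. With 10 per arm, two or three leavers are a large share of the data. The trial's stated use is to supply estimates for sizing the next trial, so a shifted estimate carries forward.

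**Working it through.** **Plan's own figure.** The sample size is 2 × 10 = 20, justified by feasibility. No effect size, SD, correlation, power or dropout rate is given, so everything below rests on assumptions.

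**Step 1: what the change test loses.** Assume 2 of 10 per arm have no post value. Going from 10 to 8 per arm (two-sided 0.05, noncentral t) raises the standardised difference detectable at 80% power from 1.32 to 1.51, and lowers power at a difference of 1 SD from 0.56 to 0.46.

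**Step 2: precision when leaving is random.** Assume SD 1, n = 10 randomised and m = 8 with week 6 per arm, leavers seen through week 4, no close-out value, and equal correlation r = 0.5 between visits.

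- Completers' change: SE = √[2 × 2(1 − r)/m] = √(2/8) = 0.500.
- Two-point likelihood model: variance per arm = (1 − r²)/m + (1 − r)²/n = 0.75/8 + 0.25/10 = 0.11875; SE = √0.2375 = 0.487.
- Model with weeks 0, 2, 4, 6: regressing week 6 on the three earlier visits gives each coefficient r/(1 + 2r) = 0.25 and residual variance 1 − 3r²/(1 + 2r) = 0.625. The weights on weeks 0, 2, 4 are −0.75, 0.25, 0.25, with variance 0.6875 − 0.3125 = 0.375. Variance per arm = 0.625/8 + 0.375/10 = 0.115625; SE = √0.23125 = 0.481.

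The other structures, in the same order, gave:

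- equal correlation 0.3: 0.592, 0.571, 0.567
- equal correlation 0.7: 0.387, 0.381, 0.373
- first-order autoregressive, 0.7 per two weeks: 0.573, 0.554, 0.537
- first-order autoregressive, 0.85 per two weeks: 0.439, 0.431, 0.410

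The interim visits therefore lower the SE by about 4 to 7% against completers and about 1 to 5% against the two-point model. With no dropout, all three SEs are equal. On the MADRS scale, a simulation with the SDs in step 3 and random dropout gave SE 4.29 without and 4.19 with the interim visits, about 2%.

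**Step 3: bias when leaving depends on early scores.** Assumed: SDs 5, 7, 8, 9 at weeks 0, 2, 4, 6; correlations 0.3 to 0.8; true week-6 difference 5; 10 per arm; about 20% without week 6. In the first pattern only sham leaving depends on response and iTBS leaving is random (about 25% v 19% where recorded). In the second, the same dependence applies in both arms. The set-ups are separate simulations of these patterns. Mean estimates:

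| Pattern | Set-up | Completers' change | Two-point likelihood model | With weeks 2 and 4 |
|---|---|---|---|---|
| Sham only | 1 | 3.5 | not run | 5.0 |
| Sham only | 2 | 3.1 | 3.2 | 5.1 |
| Sham only | 3 | 2.7 | 2.9 | 5.05 |
| Both arms | 1 | 4.7 | not run | 5.0 |
| Both arms | 2 | 4.3 | 4.3 | 5.1 |
| Both arms | 3 | 4.3 | 4.4 | 5.1 |

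With 5,000 trials the simulation error is about 4.29/√5000 = 0.06. At 500 per arm, set-up 2 (sham only) gave 2.9, 3.0 and 4.9, so this is not a small-sample effect. Keeping baseline-only subjects barely moves the estimate; adding the interim scores removes the bias.

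**Step 4: adding the close-out visit.** A fourth set-up assumed that every leaver attends close-out, scores the week-4 value there, and has it entered as post-intervention. For sham-only leaving it gave 4.83, against 2.50 for completers, 2.68 for the two-point model and 4.95 with interim visits. For the shared pattern it gave 4.86, against 4.41 for completers and 4.99 with interim visits. The completers' 2.50 shows that the lower end of the sham-only range is not sharp.

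**Step 5: consequence for planning.** Required sample size scales with (true/estimated)². This is (5/4.7)² = 1.13 to (5/4.3)² = 1.35 for the shared pattern, and (5/3.5)² = 2.04 to (5/2.7)² = 3.43 for the sham-only pattern.

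**The case against.** A reader might infer that an early leaver contributes nothing to the depression result and that the intention-to-treat commitment is broken outright. The documents do not support that. A subject who attends close-out has a post value and enters both analyses. A subject with only a baseline stays in a mixed model fitted by likelihood. F does not list the levels of time, and its baseline-to-post wording sits in one paragraph that also covers Toolbox and imaging, which have only two time points. The interim scores are unmentioned, not expressly excluded. The commitment to use all data is made in 2.h; F itself promises only intention-to-treat principles.

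A reader might also take a loss of 30% or more of the effect as the expected bias. That needs sham non-improvers to leave because of non-response while iTBS subjects leave at random, with no close-out data. Nothing in the documents points to arm-specific leaving in this blinded design. Under a shared mechanism the bias is 0.3 to 0.7 points against an SE above 4.

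These objections limit the size and the wording but do not close the gap. The close-out visit is worded for subjects who decide to withdraw, not for those terminated by the investigator, such as after hospitalisation or too many missed sessions. F has no rule for its timing, so an early score could be entered as if it were week 6. Full attendance, as in step 4, is optimistic. The two-point mixed model does not remove the bias.

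**Conclusion.** The point holds as a gap in specification that has a better method available. MADRS is collected at weeks 2, 4 and 6, no stated analysis is said to use weeks 2 and 4, and the 2.h commitment is not carried into F.

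The size depends on why subjects leave. With about 20% missing week 6, a true difference of 5 and no close-out data:

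- **Leaving depends on early response in both arms:** two-point estimate about 4.3 to 4.7, a shortfall of 6 to 14%.
- **Leaving depends on it only under sham:** about 2.7 to 3.5, a shortfall of 30 to 46%.
- **Leaving is random:** no bias, and a gain of only a few percent in SE.

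Close-out values would shrink the shortfall to the extent that leavers attend. The main gain is a prespecified analysis that keeps every randomised subject and uses the scores already collected; the precision gain is modest.

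**What to change.** In F, make the MADRS analysis a likelihood-based repeated-measures mixed model on baseline and weeks 2, 4 and 6 for all randomised subjects, with the week-6 arm contrast as the depression test. Prespecify the covariance structure, name a simpler fallback in case it does not converge with 20 subjects, and use small-sample degrees of freedom such as Kenward-Roger. Enter a close-out MADRS at the visit nearest the time it was taken, not automatically as week 6. State the missing-data assumption. Report the change-score test as supportive.

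The cost is SAP wording and a few lines in the SAS software that F already names, with no new data. There are three limits. A covariance structure must be fixed in advance for a small sample. The correction relies on leaving depending on observed scores. It does nothing for Toolbox or fMRI, which have no interim values.

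### Does the two-way iTBS-by-Fazekas term test the wrong quantity when the question is modification of connectivity change?

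*Combined protocol and SAP*

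**What the plan says.** Everything on this point is in section F (Statistical Plan).

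- **The modification sentence.** "Through the 2-way interaction iTBS*Fazekas score we will explore the modification effect of grade of white matter burden on the impact of iTBS". The sentence then names what is being modified: "on the impact of iTBS in the observed network connectivity changes". It does not name the response variable or write out the model.
- **The model.** "We will use a mixed general linear model (GLM) to accommodate data from our within- and between-participant study design".
- **The treatment effect in that model.** "Differences between groups in behavioral outcome measures and network connection changes will be evaluated through 2-way interaction effect (time*group").
- **Change scores as responses.** The opening t-tests (or their non-parametric equivalents) compare "the changes in the main outcome measures between active and sham groups". Later in the section, changes in behaviour are correlated with changes in connectivity, and the mediator in the PROCESS analysis is a pre-minus-post difference in connection strength.
- **Test level.** "All statistical tests will be two-sided and evaluated at the alpha level of 0.05".
- **Size.** The pilot enrols 20 people and has "randomized them to iTBS arm or placebo arm (10 in each group"). The number is justified by feasibility, with no effect size or power.

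Connectivity is scanned twice, before and after the intervention (A1 Study Abstract; E4 Study Outcome Measurements and Ascertainment). The Fazekas score is not mentioned in the aims (A2, C1, C2) or among the outcomes in E4.

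**The concern.** The sentence just before the Fazekas sentence takes the treatment effect on connectivity to be time-by-group, which is already a two-way interaction. Modification of a two-way effect by a third variable is a three-way term, yet the plan again writes two-way.

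Taken literally in the repeated-measures model, a group-by-Fazekas term says how the Fazekas slope differs between arms at baseline or averaged over both scans, depending on the coding. One of the two scans precedes any stimulation. A real modification would be diluted, and chance differences in the first scan would enter the estimate. Because the pilot is meant to inform a later grant application, a diluted estimate could be carried into the next design.

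**Working it through.** The plan gives no effect size, power or moderation figure, so there is nothing of its own to reproduce. The check has three parts.

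**1. What each term estimates**

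Let g be arm (0/1), F the Fazekas grade and θ the true modification at the post scan. Randomisation makes the expected group-by-Fazekas coefficient zero at baseline.

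| Response or term | Expected coefficient |
|---|---|
| Change (post − pre), group-by-Fazekas | θ − 0 = θ |
| Repeated scans, three-way term | θ − 0 = θ |
| Mean of both scans, group-by-Fazekas | (0 + θ)/2 = θ/2 |
| Repeated scans with the three-way term and baseline as reference, group-by-Fazekas | 0 |

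The first two rows are the same estimator with two complete scans.

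**2. Size, by simulation**

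From the plan: 10 per arm, two scans, two-sided 0.05. Assumed, since the plan is silent: Fazekas grades 0 to 3 with probabilities 0.25, 0.35, 0.25 and 0.15; SD 1 at each scan; pre/post correlation ρ of 0.3, 0.5 or 0.7; θ = 1 SD per grade; ordinary least squares; 3,000 trials per setting.

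| Analysis | Mean estimate (ρ = 0.3 / 0.5 / 0.7) | Power |
|---|---|---|
| Group-by-Fazekas on change, or the three-way term | 1.01 / 1.00 / 1.02 | 0.38 / 0.48 / 0.71 |
| Group-by-Fazekas on post, adjusted for baseline | 1.01 / 1.00 / 1.01 | 0.50 / 0.57 / 0.74 |
| Group-by-Fazekas averaged over scans | 0.51 / 0.50 / 0.49 | 0.23 / 0.19 / 0.20 |

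The change-score and three-way estimates agreed in every run (largest difference about 3e-14).

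The loss of power in the last row follows from the variances. The mean of two scans has variance (1 + ρ)/2 and the change has variance 2(1 − ρ). The ratio of signal to noise is therefore [(θ/2)/√((1 + ρ)/2)] ÷ [θ/√(2(1 − ρ))] = √((1 − ρ)/(1 + ρ)), which is 0.73, 0.58 and 0.42 for the three correlations.

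One half is not a general figure. With generalised least squares, no three-way term and unequal variances, the share recovered was 0.10 to 0.32 when the post/pre SD ratio was 1.3, and 0.66 to 0.85 when it was 0.8.

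With θ = 0 and 10 per arm, rejection rates were 0.042 to 0.052 for every term tested. Chance baseline differences enter both candidate estimates. The correlation with the pre-scan interaction is √((1 + ρ)/2) = 0.81, 0.87, 0.92 for the averaged term and −√((1 − ρ)/2) = −0.59, −0.50, −0.39 for the change term.

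**3. Which response the text supports**

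For change: the modification sentence is about changes in connectivity, and three other analyses in section F (group comparison, correlation, mediation) take change as the variable. A change-score model has no time factor, so group-by-Fazekas is correctly called two-way.

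For repeated scans: the preceding sentence also speaks of changes in connections, yet assigns them to time-by-group.

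The wording does not settle it. It leaves the response unnamed, which is different from prescribing a wrong test.

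**The case for a change.** The best case for amending runs as follows. The plan treats time as a factor when it defines the treatment effect, and by its own way of counting, the modification must be three-way. That term appears nowhere, and no other section supplies the response. Someone following the text to the letter could report anything from nearly nothing to the full effect. One sentence, at no data cost, would remove a choice otherwise made after the data are seen.

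The algebra in this argument stands, and so does the observation that the response is not named. The step from there to a required change does not. The poor result needs an analyst who fits group-by-Fazekas to the repeated scans and then reports it as modification of change, although the sentence itself asks about change. An analyst who stays in the repeated-measures model and has just read the treatment effect from time-by-group has every reason to carry time into the modification term as well. An analyst who uses change scores gets the same number from the two-way term. Adjusting the post scan for baseline is a different estimator with the same target, and it is also sound.

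**Conclusion.** No change to the plan is called for. Read with change as the response, the stated term is right and loses nothing. Read against repeated scans, the matching term is the three-way one, which gives the identical estimate. What is missing is the name of the response for one exploratory term, a detail that a competent analyst supplies.

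Under the least favourable literal reading with equal variances and averaging over scans, the estimate is halved and power with 10 per arm is roughly 0.2, against 0.38 to 0.71. Those figures rest on the assumed Fazekas distribution, a modification of 1 SD per grade and correlations of 0.3 to 0.7, none of which the plan gives. Even then the false-positive rate stays near 0.05, so the harm is dilution rather than spurious findings. None of the three aims or the listed outcomes depends on this term, and a 20-person pilot sized on feasibility can say little about modification whichever form is fitted.

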C1 Primary Aim

Aim 1. To assess the efficacy of iTBS in improving mood and executive dysfunction in older

adults with depression. Hypothesis 1. Older adults randomized to iTBS will show significant decreases in the Montgomery Asberg Depression Rating Scale consistent with improvement, and significant increases in scores on the NIH Toolbox executive domain measures consistent with executive function improvement compared to those subjects randomized to placebo stimulation (sham).

C2 Secondary Aims

Aim 2. To test the effects of iTBS on functional connectivity within the Cognitive Control Network (CCN) in depressed older adults using resting state fMRI. H_2 Depressed older adults randomized to iTBS versus sham will have a significant increase in functional connectivity within the CCN.

Aim 3. To examine the association between change in clinical symptoms and neurocognitive assessments and changes on brain connectivity within the CCN. H_3 Among older adults who receive iTBS, changes in connectivity within the CCN will correlate with changes in depression and executive function.

C3 Rationale for the Selection of Outcome Measures

Depression Measure:

The Montgomery-Asberg Depression Rating Scale, is a standardized mood rating scale, widely used in depression studies. The scale is particularly sensitive to treatment effects, demonstrating greater sensitivity to change (between responders and non-responders) to antidepressant treatment than other scales such as the Hamilton Depression Rating Scale.

Executive function measures:

The flanker inhibitory control, the Dimensional Change Card sort test and the List Sorting Working memory test will measure executive function. These scales are state of the art scales and are recommended by the National Institutes of Health in their NIH Toolbox. NIH Toolbox measures are brief and standardized for assessing function from ages 3 to 85. The NIH toolbox monitors behavioral function over time and across developmental stages. This makes it possible to study changes across the lifespan, and evaluate the effectiveness of a treatment.

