The PI [name] and her designee will meet weekly for research meetings to focus on screening forms; inclusion/exclusion criteria; case report form review; adverse events and other Human Research Protection Office (HRPO) required monitoring and reporting activities. The PI or her designee will record each subject screened for study inclusion and maintain records of reasons for subject exclusions. This information will be included in yearly renewals with the HRPO.

[name] (Professor at the Department of Psychiatry) will be fully available to provide guidance regarding issues related to the safety of study participants and the integrity of the study. [name] will participate in research meetings to review accuracy of screening, subject accrual, and all subjects who withdraw from the study. Likewise, he will be available to assess with issues regarding participant accrual, overall study progress, intervention efficacy, adverse events, ethical concerns, quality of monitoring, and protocol adherence. The entire investigative team with [name] , [name] and the PI Designee will meet at least once per quarter.

We will follow procedures pertaining to adverse events and serious adverse events as specified in the DSMP document

E4 Study Outcome Measurements and Ascertainment

Primary outcome measures:

The effects of the study intervention depression will be measured using the Montgomery Asberg Depression Rating Scale.

The effects of the study intervention on executive function will be evaluated using the Flanker inhibitory control, the Dimensional change sort task and the List Sorting Working memory test will measure executive function, from the NIH Tool box executive function domain.

Brain's connectivity measure: Using resting state fMRI we will measure functional connectivity within the Cognitive Control Network (CCN) in depressed older adults before and after study intervention. We will also explore functional connectivity within and between other networks that are relevant to depression including the Default Mode network and the cingulo-opercular networks.

F Statistical Plan

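### Does Section F leave open who enters the Aim 3 correlation and how the exploratory Fazekas term is fitted?

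*Combined protocol and SAP*

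**What the plan says.** Aim 3 (Sections A2 and C2) is worded generally: "To examine the association between change in clinical symptoms and neurocognitive assessments and changes on brain connectivity within the CCN". H3 follows at once and is specific: "Among older adults who receive iTBS, changes in connectivity within the CCN will correlate with changes in depression and executive function".

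Section F gives one sentence of method for this aim. After naming Pearson, it reads "correlation will examine the correlation between changes in behavioral measures with changes in network connectivity". It states no arm, no adjustment for arm and no particular network. The section opens with "We will use intention-to-treat principles" and gives the sample as 20 subjects, "randomized them to iTBS arm or placebo arm (10 in each group", justified by feasibility. All tests are two-sided at 0.05.

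On other networks, Sections C3 and E4 say "We will also explore functional connectivity within and between other networks that are relevant to depression".

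On white matter, Section F proposes a two-way iTBS-by-Fazekas interaction to "explore the modification effect of grade of white matter burden on the impact of iTBS in the observed network connectivity changes". The Fazekas score is mentioned nowhere else in the text supplied. For the mediation analysis, Section F treats change in connection strength "as mediator of change for iTBS and bootstrap and Monte Carlo confidence intervals will be calculated"; it promises no interval for the correlation.

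**The concern.** Taken alone, Section F allows two analyses of Aim 3: a correlation in 10 iTBS recipients, or one in all 20 subjects. They have different critical values and answer different questions. If iTBS shifts both mood and connectivity, as H1 and H2 predict, a pooled correlation that ignores arm picks up the arm difference even when the two changes are unrelated within each arm. An analyst who had seen the data could choose either reading and cite the protocol for it. The pilot is meant to inform a later grant, so a correlation of unclear population would carry forward poorly.

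The Fazekas sentence raises a similar doubt. It comes just after a mixed model in which change is the time-by-group term. In that model, modification of a change needs a three-way term, whereas Section F names a two-way one. The assessment lists in Section E2 contain no Fazekas rating.

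**Working it through.** The plan gives no effect size, correlation or power for this aim, so there is no figure to reproduce. The check has three parts.

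**1. Reading Aim and hypothesis together.** The same drafting pattern holds for all three aims.

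| | Aim sentence | Hypothesis sentence |
|---|---|---|
| 1 | efficacy of iTBS; no comparator | adds the comparison with sham |
| 2 | effect of iTBS on CCN connectivity; no comparator | adds iTBS versus sham |
| 3 | association of changes with CCN connectivity; no arm | adds iTBS recipients only |

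The aim gives the topic and the hypothesis gives the test. Aim 3 without an arm does not compete with H3, just as Aim 1 without a comparator does not compete with H1. The Pearson sentence is the method for H3, so the population is the iTBS arm and the network is the CCN. Other networks are already labelled as exploration in Sections C3 and E4.

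**2. What the choice of population would do.** Inputs from Section F: 10 per arm, two-sided 0.05. Assumptions: complete data, bivariate normal changes, and iTBS shifting both changes by the same d (in SD units).

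Critical value: |r| = t/√(n − 2 + t²).
- iTBS only, n = 10: t = 2.306 on 8 df, so 2.306/√(8 + 5.318) = 0.632.
- Pooled, n = 20: t = 2.101 on 18 df, so 2.101/√(18 + 4.414) = 0.444.

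With no within-arm link, the pooled correlation tends to (d²/4)/(1 + d²/4). At d = 1.0 this is 0.25/1.25 = 0.20. Rejection and disagreement rates come from simulation.

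| d on both changes | Pooled r expected | iTBS-only rejects | Pooled rejects | Verdicts differ |
|---|---|---|---|---|
| 0 | 0 | 5% | 5% | 7% |
| 0.5 | 0.06 | 5% | 5.7% | 8% |
| 0.8 | 0.14 | 5% | 9% | 11% |
| 1.0 | 0.20 | 5% | 14% | 16% |
| 1.5 | 0.36 | 5% | 38% | 38% |

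If only one of the two measures shifts (by 1.0 SD), the pooled test also stays at 5%. The iTBS-only test that H3 describes holds its level in every row. Its cost is precision. The Fisher interval is tanh(atanh r ± 1.96/√(n − 3)). At an observed r of 0.5 and n = 10, this is tanh(0.549 ± 0.741), or −0.19 to 0.86. Power at a true r of 0.5 is 33%.

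**3. The Fazekas term.** Let the modification be δ per grade, absent before treatment and present after it. On the change score the two-way coefficient is δ − 0 = δ. If pre and post values were stacked and the two-way term fitted without time, it would average the two occasions: (0 + δ)/2 = δ/2. Simulation agrees: with assumed δ of 0.2, 0.4 and 0.6, the change-score means were 0.20–0.21, 0.39–0.41 and 0.58–0.63, and the stacked estimate was 0.45 to 0.52 of the change-score estimate. Section F names connectivity changes as the target, which is the first case.

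**The case for a change.** The strongest opposing case is that Section F is where an analyst looks, and it does not repeat the restriction in H3. The choice matters most if the trial's own hypotheses are right. With a within-arm correlation of 0.5 under iTBS and 0 under sham, the two readings reach different verdicts in 25% of trials with no shift and 48% at 1.5 SD. With 0.5 in both arms, they differ in 37% to 63%. One added sentence would remove the ambiguity at almost no cost, and at n = 10 an interval says more than a p-value.

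The arithmetic stands, and so does the observation that Section F names no arm. It does not follow that the plan is open. The disagreement rates compare the analysis H3 describes with one that the plan does not specify. Where there is no link and little shift, the 7% to 8% is essentially chance disagreement between two tests at or near their nominal level. The intention-to-treat statement is general and does not override a hypothesis that names its own population. An interval for the correlation, or an arm-adjusted supportive estimate, is a reporting preference that an analyst can add without amending anything.

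On Fazekas, it is true that no section says which scan is rated or by whom. Absence from Section E2 is weak evidence of an omission, however. Those lists name the MRI visits but no image-derived measure, and CCN connectivity is not listed there either. Section D3 uses subjects' structural MRI scans for targeting, so structural images exist.

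**Conclusion.** No change follows. The gap is one of wording: Section F omits a restriction that the protocol states in both A2 and C2. Following the plan as written, with H3 read alongside F, gives a correlation in the iTBS arm with a 5% error rate and a Fazekas interaction on connectivity change that is unbiased. Inflation to between 5.7% and 38% arises only under a pooled, unadjusted correlation with assumed shifts of 0.5 to 1.5 SD on both measures. Halving of the Fazekas effect arises only under a stacked model that Section F does not describe.

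The stakes are also small. Aim 3 is secondary, the Fazekas analysis is exploratory, and the sample was set by feasibility. Analysts should note that n = 10 is a best case: the close-out visit for withdrawn subjects (Section D2, 2.h) covers mood and executive assessments and mentions no scan, so some connectivity changes may be missing. A report that states the arm, the number of complete pairs and the scan used for the Fazekas rating would settle what is left. The conclusion rests on reading each hypothesis as specifying its aim, which is how all three are drafted.
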